14. PRACTICAL USE OF THE RESULTS

The progressive aging of our population carries an increasing prevalence of degenerative aortic valve stenosis in our country, constituting a public health problem

of crucial importance. There is scientific evidence that amyloidosis is an underdiagnosed disease in clinical practice, which coexists simultaneously in a large number of patients suffering from aortic stenosis, and that could overshadow the prognosis. To determine the prevalence and prognostic impact of amyloidosis referred for percutaneous implantation of an aortic prosthesis is important in order to understand the interrelationship of both diseases. This information will guide us to take the appropriate measures in need of a screening and the early treatment that will allow optimizing the resources available.

15. ETHICAL CONSIDERATIONS

The project will be made in compliance with the Declaration of Helsinki (Annex III) of the 1964 World Medical Association 1964 and ratifications of the following assemblies (Tokyo 75, Venice 83, Hong Kong 89, Somerset West 96, Scotland 00, Seoul 08 and Fortaleza 13) on ethical principles for medical research on human beings, the RD 1090/2015, of 24 December, clinical trials, specifically that stipulated in Article 38 on good clinical practice and the Agreement related to human rights and biomedicine), made in Oviedo the 4 of April 1997 and subsequent updates.

The participating researchers in this study undertake that all clinical data collected from the study subjects are separated from the personal identification data so that the anonymity of the patient is ensured; respecting the law on Personal Data Protection (Organic Law 15/1999, 13 of December), the RD 1720/2007 of 21 of December, approving the Regulations implementing the Organic Law 15/1999, the Law 41/2002, of 14 of November (regulating the autonomy of the patient, rights and obligations regarding clinical information and documentation), as well as Law 3/2001, of 28 of May, (regulating the informed consent and medical history of the patients), the Law 3/2005, of 7 of March, modification of Law 3/2001 and the 29/2009 Decree of 5 of February, by which electronic access to medical histories is regulated.

The clinical data of patients will be collected by the researcher in the Data Collection Logbook (DCL) specific to the study. Each DCL will be coded, protecting the identity of the patient. Only the research team and health authorities, who have a duty to maintain confidentiality, have access to all the data collected for the study. Third parties may only be provided with information that is not identified. Once the study is completed, the data will be destroyed.

Sample handling will follow what is established in Law 14/2007 of 3 of July for Biomedical Research, in the RD 1301/2006, of 10 of November, establishing the

Prognostic impact of cardiac amyloidosis in patients with severe aortic stenosis who
underwent percutaneous implantation of an aortic prosthesis

regulations for quality and safety for the donation, procurement, evaluation, processing, preservation, storage and distribution of human cells and tissues and abiding the regulations for coordination and functioning for its use on humans and in the RD 1716/2011, of 18 of November, establishing the basic requirements for authorisation and functioning of biobanks for biomedical research and treatment of biological samples of human origin, and the functioning and National Registry of Biobanks for the biomedical research is regulated.

The treatment, communication, and transfer of data will be done according to what is stated in the General Data Protection Regulation (Regulation (UE) 2016/679 of the European Parliament and the Council, of 27 of April 2016). The center, where the information is obtained, is responsible for processing the data. The data collected will only be used for the purposes of the research study described in the protocol and maintained for the time needed to achieve the study objectives and in accordance with the applicable law.

ANNEX I: ECHOCARDIOGRAPHIC STUDY

SUGGESTIVE ECHOCARDIOGRAPHIC FINDINGS:

Cardiac involvement is generally characterized by the presence of an infiltrative/restrictive myocardopathy with conventional echocardiographic findings that have been well described, but also with new echocardiographic findings identified using echocardiographic strain techniques. The main suggestive findings are:

- Increased wall thickness ≥ 12 mm with a myocardium of a shiny appearance, refractile, granular or mottled (“sparkling”), resulting from the deposits of amyloid fibrils which are more echogenic than a normal myocardium; wall thickening VI medium > 15 mm was an independent factor associated with a worse prognosis.
- Normal or small left ventricular cavity.
- Ejection fraction of VI (FEVI) preserved or borderline $> 50\%$ (at least in the early stages of the disease; depressed in advanced stages)
- Tissue Doppler: waves S' and E' reduced to basal level of the septal or lateral myocardium, reflecting a depressed longitudinal and an altered relaxation of VI.
- Abnormal mitral filling pattern: from diastolic dysfunction of VI mild or moderate (transmitral pattern type I or II); and in advanced stages, a typical restrictive transmitral pattern, with a ratio E/A > 2 , E/E' increased, and small wave A due to the atrial dysfunction.
- The high filling pressure of VI may gradually lead to enlargement of the left atrium (diameter > 23 mm/m²; area > 20 cm² or maximum volume > 28 ml/m²), which is useful for the differential diagnosis and it is also an independent factor associated with worse prognosis in AL.
- Enlarged right atrium and dilated inferior vena cava, reflecting the filling pressure of the right ventricle (RV).
- Increased thickness of the interatrial septum (this variable is much easier to measure in cardiac magnetic resonance (MRI) than in echocardiography).
- Wall thickness free of increased RV (> 7 mm), with systolic and diastolic dysfunction of RV, associated with worse survival.
- Thickening of the left and right valves, generally responsible for light insufficiencies.

- Reduced aortic ejection time (< 273 ms), described as a prognostic factor.
- Mild pericardial effusion in 50% of the cases. The presence of effusion is an independent factor associated with worse survival;
- Atrial thrombus can be found despite maintaining a sinus rhythm;

ACQUISITION PROTOCOL

Acquire 3 beats in sinus rhythm and 5 beats in Atrial Fibrillation.

Ensure good ECG signal.

For Doppler curves, use adjusted scales to the corresponding valve gradients, scan speed 75 mm/s.

Optimize sector width, gain, and compression to ensure maximum image quality.

Do not perform any measurement in the study to be sent to the Core Lab (only the collection of images and imaging loops)

Parasternal long axis (PLAX):

2D

Colour in mitral valve and aortic valve

2D Zoom in aortic valve

If aortic insufficiency: zoom color in the aortic valve.

Mode M in aortic valve

Modo M in VI

Parasternal short axis (PSAX).

2D

Zoom 2D in aortic valve

Colour in the aortic valve.

Zoom 2D in pulmonary valve

Colour in the pulmonary valve

Pulsed Doppler in the pulmonary valve

Colour in the pulmonary valve

Colour in tricuspid valve

Continuous Doppler in tricuspid valve

Mode M in aortic valve and in VI (if PLAX has not been performed)

Parasternal in Right Cavities.

2D

Colour Doppler in the tricuspid valve.

Continuous Doppler in the tricuspid valve.

Apical 4C:

2D

2D with extended left Ventricle

Colour Doppler in Mitral Valve

Pulsed Doppler in Mitral Valve

Pulsed Tissue Doppler in septal and lateral Mitral annulus.

Continuous Doppler in Mitral Valve, if significant insufficiency

Zoom color with PISA scale in Mitral Valve, if significant insufficiency.

Colour Doppler in Tricuspid Valve

Continuous Doppler in Tricuspid Valve

Mode M in tricuspid annulus.

Pulsed Tissue Doppler in the tricuspid annulus.

3D: Acquisition of complete volume of the left ventricle (minimize the presence of artifacts and optimize profit adjustment)

3D: Acquisition of complete volume centered in the right ventricle.

Apical 5C

2D

Colour Doppler in aortic valve

Pulsed Doppler in TSVI

Continuous Doppler in aortic valve

APICAL 2C

2D

Colour Doppler in Mitral Valve.

Zoom color with PISA scale in the mitral valve, if significant insufficiency.

APICAL 3C

2D

Zoom in TSVI

Colour Doppler in aortic valve.

Prognostic impact of cardiac amyloidosis in patients with severe aortic stenosis who underwent percutaneous implantation of an aortic prosthesis

Pulsed Doppler in TSVI

Continuous Doppler in aortic valve

Colour Doppler in Mitral valve.

If significant mitral insufficiency: continuous in Mitral and zoom color with PISA scale in Mitral.

Subcostal plan

2D 4C.

Zoom VD free wall (for measuring the thickness of the right ventricle)

2D in VCI

Mode M in VCI, from basal to deep inspiration.

ACQUISITION PROTOCOL FOR ECHOCARDIOGRAPHY IMAGES FOR THE STUDY OF THE STRAIN.

Aspects of images ACQUISITION:

Configure the study to gain 3 consecutive beats in apnea. If the patient is in atrial fibrillation, acquire 5 beats, avoid extrasystole.

Use a temporary resolution /frame rate of > 50 (ideally 60-80 frames/s).

Plans for measuring of the STRAIN

Acquire imaging of left ventricle expanded in the plans apical 4C, Apical 2C, and Apical 3C, focussed on the left ventricle, ensuring a correct visualisation of the endocardial borders.

Acquire imaging of the left atrium in the plans apical 4C, apical 2C, and apical 3C, focused on the atrium, ensuring correct visualization of all the atrium borders, avoiding an auricle and pulmonary veins.

Acquire imaging centered in the right ventricle from the plan apical 4C, ensuring adequate visualization of the endocardial border of the free wall.

REFERENCES FOR ANNEX II

1. Lang RM, Badano LP, Mor-Avi V, el al. Recommendations for cardiac chamber quantification by echocardiography in adults: an update from the American

Prognostic impact of cardiac amyloidosis in patients with severe aortic stenosis who underwent percutaneous implantation of an aortic prosthesis

Society of Echocardiography and the European Association of Cardiovascular Imaging. *Eur Heart J Cardiovasc Imaging*. 2015; 16:233–270. doi: 10.1093/ehjci/jev014.

2. Pagourelas ED, et al. Echo Parameters for Differential Diagnosis in Cardiac Amyloidosis. *Circ Cardiovasc Imaging*. 2017; 10:e005588. DOI: 10.1161/CIRCIMAGING.116.005588.)
5. Phelan D, et al. Relative apical sparing of longitudinal strain using two-dimensional speckle- tracking echocardiography are both sensitive and specific for the diagnosis of cardiac amyloidosis .*Heart* 2012; 98:1442e1448. doi:10.1136/heartjnl-2012-302353
6. Bhogal S, et al. Cardiac Amyloidosis: An Updated Review With Emphasis on Diagnosis and Future Directions .*Curr Probl Cardiol* 2018; 43:10–34.

ANNEX II: SCINTIGRAPHIC STUDY

BASIC INFORMATION

Amyloidosis is a heterogeneous group of diseases in which there are abnormal extracellular insoluble fibril deposits, which are given the anatomopathological name of amyloid deposits. The amyloidosis can be classified into systemic or localized ways in an organ. Some types of this disease can infiltrate the heart, although only some types of these twenty known amyloidotic proteins produce cardiac affection. These correspond to the varieties: *senile*, *the secondary type AA*, *the primary type AL*, and some inherited ways like the one related to *transthyretin (ATTR)*, among others (*AAPoA-I* and *Afib*). Of these, the most frequently related to the heart are the ATTR and AC-AL.

The ^{99m}Tc -DPD (^{99m}Tc acid 3,3-diphosphono-1,2-propanedicarboxylic) is a bisphosphonate conventionally used in nuclear medicine for assessing bone pathology, but it has also demonstrated utility as an important technique to distinguish between the cardiac deposits in AC-TTR versus those in AC-AL, as they pose evolution, treatment and different prognoses as in the case of amyloidosis due to genetic defect with great transcendence for the family.

The cardiac scintigraphy with ^{99m}Tc -DPD is a tool that has proven useful for differentiating between the amyloidosis related with the transthyretin and the deposit by light chains of monoclonal immunoglobulin.

PATIENT PREPARATION

Previous preparation is not necessary.

Avoid caffeine and toxins like tobacco 48 hours before the study.

RADIOPHARMACEUTICALS, DOSAGE, AND ADMINISTRATION

Compound: The radiopharmaceutical used is the ^{99m}Tc -DPD. The ^{99m}Tc -MPD can also be used.

Dosage:

- Adults: 20 mCi (740 MBq).
- For children, the dosage is calculated according to the weight and the clinical guidelines in the European Society of Nuclear Medicine for the ^{99m}Tc .

Administration: intravenous.

Dosimetry: The effective dosage (E) resulting from the administration of a quantity of 700 MBq of acid 3,3-diphosphono-1,2-propanedicarboxylic labeled with technetium (^{99m}Tc) for an adult of 70 kg in weight is of 4 mSv. For an administered activity of 700 MBq, the dosage of radiation absorbed by the target organ (bone) is 44,1 mGy, and 33,6 mGy by the critical organ (bladder).

Prognostic impact of cardiac amyloidosis in patients with severe aortic stenosis who underwent percutaneous implantation of an aortic prosthesis

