8. OBJECTIVES

8.1 PRIMARY OBJECTIVE

A multicentre prospective study of cohorts consisting of two cohorts from patients who have been implanted with percutaneous aortic prosthesis as treatment for the severe degenerative aortic stenosis and compare the overall mortality and that for

cardiovascular and admissions for heart failure in the 2-year follow-up of patients diagnosed with amyloidosis (by GT99 and EFP) versus those that do not have it.

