9. DESIGN

A multicentre, analytical, observational study of two cohorts. One cohort will be constituted by the patients to whom a TAVI will be implanted, and that meet non-invasive diagnostic criteria of TTR amyloidosis (capturing of radiotracer in grades 2 and 3 and absence of monoclonal gammopathy the PE of urine or serum). The other cohort will be constituted by patients whose TAVI implants do not meet the diagnostic criteria for TTR amyloidosis.

A clinical and echocardiographic follow-up will be done in all patients for two years.

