9.3. EXCLUSION CRITERIA

- Death as a result of a complication of the procedure during hospitalization.

- An associated mitral valve requiring intervention

- TAVI implant valve-in-valve.

- Does not sign informed consent.

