11. PATIENTS FOLLOW-UPS

11.1 INITIAL PATIENT ASSESSMENT

An initial inclusion visit will assess whether the patient is a candidate who meets the inclusion criteria and none of the exclusion ones. After being informed, if they accept, the informed consent must be signed. The following data must be recorded:

- **Clinical parameters:** age, sex, height, weight, body mass index, body surface, cardiovascular risk factors, medication intake, background interests, history of heart disease, presence of ischemic heart disease, cerebrovascular accident, peripheral artery disease, chronic obstructive pulmonary disease, symptoms (angina, syncope, dyspnea according to grades of the NYHA, other symptoms), blood pressure, heart rate, evidence of heart failure, assessment of functional class by means of 6MT and fragility assessment.
- **Analytical parameters:** hematocrit, NT-proBNP, Troponin I, electrolytes, C-reactive protein, creatinine, glomerular filtrate.
- **Protein electrophoresis:** Rating presence of the monoclonal component
- **Scintigraphy with TC⁹⁹:** Assessment of values of tracer uptake.
- **Device parameters:** Type of prosthesis, dimensions, expandable/ self-expanding ball, post-dilatation.
- **ECG parameters:** Rhythm, PR duration, pacemakers, implantable cardioverter defibrillator, QRS duration.

- The 6 minute-test: All patients in the study will have a test of 6 minutes before implantation and 6 months follow-up, according to the protocol after a TAVI, in order to carry out an objective functional assessment of the functional capacity. The distance covered will be determined, the variation of oxygen saturation by means of non-invasive pulse oximetry before and after the test and the appearance of symptoms with the effort according to the Borg scale.

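### Monoclonal gammopathy bars a patient from the amyloid cohort but not from the comparator, so possible light-chain amyloid is analysed as no amyloid and can bias the mortality contrast toward no effect, by an unknown amount

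*Combined protocol and SAP*

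**What the plan says.** Section 9 (Design) defines the amyloid cohort by two conditions: "capturing of radiotracer in grades 2 and 3 and absence of monoclonal gammopathy the PE of urine or serum". The comparator is defined by default: "The other cohort will be constituted by patients whose TAVI implants do not meet the diagnostic criteria for TTR amyloidosis". It carries no electrophoresis condition of its own.

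Section 8.1 words the primary contrast more broadly, as "patients diagnosed with amyloidosis (by GT99 and EFP) versus those that do not have it", without restricting the type of amyloid.

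The four exclusion criteria in section 9.3 mention neither gammopathy nor AL amyloidosis. Section 10.1 (Statistical analysis) has no third group and no sensitivity analysis for these patients, and names no Cox covariates. They can nevertheless be identified: the initial assessment in section 11.1 includes electrophoresis ("Rating presence of the monoclonal component"), and the work plan in section 12 schedules it at baseline.

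On the biology, section 4 says that AL amyloid arises within a monoclonal gammopathy, that false-positive scans for TTR are almost all due to AL, and that amyloidosis carries a worse prognosis. The scan sensitivity of more than 99% in that section is given for TTR amyloidosis. Annex II describes the scan as "useful for differentiating between the amyloidosis related with the transthyretin and the deposit by light chains of monoclonal immunoglobulin".

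**The concern.** The electrophoresis result is used to purify one cohort only. By construction the amyloid cohort contains no gammopathy, while the comparator may contain any amount. The cohorts can therefore differ in a second condition as well as in TTR amyloidosis.

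If some of the gammopathy patients have AL amyloid, they sit in the group that the primary objective describes as free of amyloidosis. Any excess mortality they have is added to the reference group alone. That pulls the hazard ratio toward 1 in the one comparison the study is sized for.

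The same reference group would serve the strain validation (secondary objective 3), which concerns cardiac amyloidosis and is not limited to TTR. There, a light-chain heart showing the typical strain pattern would be scored as a false positive.

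**Working it through.** **1. Where each patient goes under section 9**

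| Uptake grade | No monoclonal component | Monoclonal component |
|---|---|---|
| 2–3 | Amyloid cohort | Comparator |
| 0–1 | Comparator | Comparator |

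Both cells in the right-hand column fall in the comparator. The upper one is there because of the gammopathy rule, and it is the group that section 4 ties to AL through the false-positive scans. The lower one is there by uptake grade alone, and nothing then screens it for gammopathy. Because the quoted sensitivity concerns TTR, a negative scan does not by itself rule out AL. That last step is an inference.

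**2. The plan's own sample size**

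Inputs from section 10 (Sample size): 15% with amyloidosis, two-year mortality 40% v 17%, alpha 0.05 (taken as two-sided), power 80%. The plan names no formula; Schoenfeld's is used here.

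- HR = ln(0.60)/ln(0.83) = 2.74.
- Events = (1.96 + 0.84)² / [0.15 × 0.85 × (ln 2.74)²] ≈ 61.
- Average event probability = 0.85 × 0.17 + 0.15 × 0.40 = 0.2045.
- N = 61/0.2045 = 298.3, so 299, within 3% of the stated 306.
- Losses: 306 × 1.05 = 321.3, the stated 321.

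No stated figure is wrong on this point.

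**3. Reference power**

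- Evaluable patients: 321 × 0.95 = 305. Exposed: 305 × 0.15 = 46. Comparator: 259.
- Events = 46 × 0.40 + 259 × 0.17 = 62.4; q = 46/305 = 0.151.
- Power = Φ(|ln HR| × √(events × q(1−q)) − 1.96) = 81.4%.

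**4. Illustrative dilution, taking 17% as the gammopathy-free rate**

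Let m be the share of the comparator with a monoclonal component and pm their two-year mortality. Both are assumptions. The comparator rate becomes p0 = (1−m) × 0.17 + m × pm, and HR = ln(0.60)/ln(1−p0). For m = 10% and pm = 40%, p0 = 0.193, HR = 2.38 and events = 18.4 + 259 × 0.193 = 68.4.

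| Share m (patients) | pm = 17% | pm = 25% | pm = 40% |
|---|---|---|---|
| 2% (5) | HR 2.74, 81.4% | HR 2.71, 80.8% | HR 2.66, 79.8% |
| 5% (13) | HR 2.74, 81.4% | HR 2.67, 80.0% | HR 2.55, 77.3% |
| 10% (26) | HR 2.74, 81.4% | HR 2.61, 78.6% | HR 2.38, 72.9% |

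**5. Cost of removing the group**

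With comparator size 259 × (1−m) at 17% mortality, power is still 81.3% at m = 10% (233 comparators). The 46 exposed patients limit precision, so losing comparators hardly matters.

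**6. If the 17% already includes gammopathy patients**

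Planned power is then unaffected, and the rate left after removal is (0.17 − m × pm)/(1−m). At pm = 25% this is 16.8% for m = 2% and 16.1% for m = 10%. Power after removal is 81.9% and 84.2% respectively, a gain on the planned 81.4%.

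**The case against.** The strongest reply has five parts.

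- **Mechanism.** A reader might infer that the gammopathy rule pushes scan-negative patients into the comparator. It does not. Grade 0–1 patients are outside the amyloid cohort by uptake alone, and the rule relocates only grade 2–3 patients with a monoclonal protein. This stands, and it is why the point must cover both grades.
- **Annex II.** A reader might also infer that Annex II places light-chain deposits at grade 0–1. It says only that the scan helps to tell the types apart. Its grading scale makes no reference to amyloid type, and section 4 puts some AL among positive scans. This stands: scan-negative AL is plausible here but not documented.
- **Gammopathy is not AL.** Section 4 says AL arises within a gammopathy, not that gammopathy implies AL. The documents report no excess mortality for gammopathy without amyloid. This stands, so the bias is conditional.
- **Size.** The 17% is described as mortality after TAVI, not as a gammopathy-free rate. If it comes from unselected patients, adding an excess on top counts that excess twice. This stands, and it rules out any claim that the study is shown to be underpowered for this reason.
- **Choice of contrast.** Comparing TTR amyloidosis with all other TAVI patients is coherent, and secondary objective 2 does name TTR. But the primary objective contrasts amyloidosis with its absence, and a comparator that may hold AL patients does not deliver that.

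The contents list also names a section on diagnostic criteria for amyloidosis that does not appear in the text available, where 9.4 is informed consent. A rule placed there cannot be ruled out.

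**Conclusion.** The asymmetry is explicit in section 9, and nothing in the exclusion criteria or the analysis plan corrects it. Following the plan exactly, every patient with a monoclonal component is analysed as not having amyloidosis. If these patients die more often than the other comparators, the hazard ratio is biased toward no effect, and the comparator does not match the primary objective.

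The size is unknown. The illustrative power range runs from no loss (mortality equal to 17%) to 72.9% (a 10% share dying at the 40% rate). It depends on an assumed share, an assumed mortality and the reading of 17% as gammopathy-free. On the other reading, planned power is intact and removing these patients is a modest gain. Either way, a symmetric restriction is a cheap improvement that needs no new data. The documents do not support a stronger conclusion, whether that AL is present in a known proportion, that it sits at grade 0–1, or that the sample size fails because of it.

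**What to change.** - **Section 9:** apply the electrophoresis condition to both cohorts in the main comparison. Exposed: uptake grade 2–3 without a monoclonal component. Comparator: uptake grade 0–1 without a monoclonal component.
- **Section 10.1 (Statistical analysis):** report all patients with a monoclonal component as a separate descriptive group, split into grade 0–1 and grade 2–3, so that neither subgroup is left unassigned. Add a sensitivity analysis that returns both subgroups to the comparator as section 9 now defines it.
- **Section 8, secondary objective 3:** use the same restricted reference group for the strain validation.
- **Section 8.1 (Primary objective):** align the wording with the cohorts actually compared.

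Make these changes before outcomes are examined, so that the placing of these patients cannot look chosen after the fact.

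Cost: text edits in sections 8, 9 and 10.1, with electrophoresis already scheduled at baseline. The comparator becomes slightly smaller, at most about 0.1 point of power in the cases shown (81.4% to 81.3%), and the main result applies to patients without gammopathy.
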